“Best Practices for End-of-life Care and Comfort Care Order Sets for Our Nation's Veterans” (BEACON) is a recently completed real-world implementation trial designed to evaluate the Comfort Care Education Intervention in six VAMCs in the Southeastern US. The Comfort Care Education Intervention consisted of two weeks of in-person staff training plus supporting written materials (pocket cards and book), creation of a CCOS in each site's CPRS system, and follow-up consultation. Staff training targeted hundreds of VAMC staff members in teaching basic palliative care, identification of the dying veteran, and application of the CCOS modified as needed for individual patients. Several processes of care were identified as quality endpoints for end-of-life care (last 7 days) and abstracted from the electronic medical records of veterans who died before or after intervention in the participating VAMCs. Primary endpoints were proportion of patients with an order for opioid pain medication at time of death, do-not-resuscitate order, location of death, nasogastric tube, intravenous line infusing, and physical restraints. Due to the possibility that secular trends could bias or confound intervention estimates, records were abstracted across the entire 6-year study period for all hospitals ($n=6,066$). Generalized estimating equations were conducted adjusting for longitudinal trends over the 6 years of the study.

[figure not shown]
Each of the intervention components was delivered to all sites. Sign-in sheets documented that training was attended by at least 1,621 staff, including 131 physicians, residents, and medical students, 66 physician

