PCCT teams at 50 VA Medical Centers will be recruited to participate in the trial. To avoid ceiling effects, recruitment will be preferential, targeting teams at sites with the lower scores on the PROMISE family after-death survey, which measures several parameters of family satisfaction with care received by the veteran. To avoid enrolling sites that might be especially resistant to change, teams at VAMCs with scores in the lowest 10th percentile will not be recruited. To compensate for potential dropout, 50 sites will be recruited to ensure the participation of 48 VA Medical Centers. The study will be announced on the twice monthly calls held with the Palliative Care Coordinators for each VISN. Emails will also be used to announce the study and invite participation. (See letter of support from [name], DO, National Director of Hospice & Palliative Care) Currently, the Comprehensive End-of-Life Care (CELC) palliative care programs have a high profile among VISN and VAMC leadership. All VISNs and VAMCs are receiving quarterly PROMISE reports, which document deficiencies in quality of care, and identifying areas that need improvement and is expected to increase facilities' motivation to participate in the study. **Each PCCT can decide individually** if they wish to participate in the study. If there is not a prescribing provider from the PCCT (enabling use of the CCOS) who wishes to participate, that site will not be included in the trial.

Once the PCCT members are identified as participants, their personally identifiable, i.e., name, telephone, email, will be maintained on VA secure networks. If paper copies exist, they will be maintained within locked office of the GRECC.

Power

Power calculations were based on data on the primary endpoint from the BEACON study, change in proportion of patients with an active opioid order at time of death. Sample sizes of 2400 patients in the Basic Implementation Approach and 2400 patients in the Enhanced Implementation Approach, which will be obtained by randomizing 24 PCCTs from VA Medical Centers with 100 patients on average to each group, will achieve 86% power to detect a difference between the group proportions of 0.05, where the proportion of patients post-intervention with an active order for opioid at death in the Basic group is 0.65 and the proportion in the

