Endpoints. The **primary endpoint** will be presence of an active order for opioid medication at the time of death. Opioids are important medicines for the management of pain and dyspnea at life's end. These medicines should be routinely available for treatment of symptom exacerbations. Numerous studies have documented that patients dying in the acute care setting are likely to have poorly controlled pain as reported by their families. **Secondary endpoints** will be other processes of care that represent the development of a comprehensive care plan for actively dying patients, including orders for and administration of appropriate medications, as well as orders that implement goals of care, palliative care consultation, orders to facilitate environmental changes that enhance patient safety and comfort, and psycho-social-spiritual support for patient and family.

Orders for and administration of appropriate medications. In addition to the primary endpoint, we will abstract orders for and administration of antipsychotic medications for delirium or nausea and vomiting,

benzodiazepines for anxiety and treatment or prevention of seizures, and medication to control excessive secretions (death rattle). While orders are necessary, they are not sufficient. If patients are in pain or have dyspnea, then the nursing services would need to administer the medication. There are numerous barriers to opioid administration, which this education intervention is designed to overcome by encouraging clinicians to write orders for opioids and schedule dosing as "offer and patient may refuse" or "nurse will assess for symptoms with option to hold," as opposed to PRN. This approach prompts the nursing staff to frequently assess for pain and dyspnea and guides them in offering small but effective doses frequently if necessary. The educational intervention is designed to relieve opioid phobia and excessive anxiety associated with the unfounded fear that small doses will cause death in dying patients. Also, it is important that the orders are flexible, so that if the patient is not able to swallow a tablet, sublingual or parental medication is available. Finally the subcutaneous route is promoted since starting and maintaining an IV is difficult for many patients at end-of-life. The subcutaneous route offers an easy to place, less painful and effective route for parenteral opioid administration, insuring that lack of IV assess is not a barrier to pain control

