The fourth aim is to assess the downstream effect of the intervention on providers at all sites who receive training from PCCT members, including their perceptions of the usefulness of the training and its impact on knowledge, attitudes, skills, self-efficacy for ordering appropriate care, readiness to use the CCOS, and practice patterns. Separate questionnaires will be developed for prescribers (who can potentially use the CCOS) and for non-prescribers (who can potentially facilitate the identification of patients who are dying and assist knowledgeably in the delivery of Comfort Care interventions). Individual providers will be identified from the sign-in sheets used by PCCT trainers in both groups and invited via email to complete a questionnaire. Two reminders will be sent to non-responders to optimize response rates. Participation will be voluntary and confidential. Specifically, these providers' supervisors and co-workers will not be informed of their participation (or non-participation) or their responses to the questionnaires. The sign-in sheets will also provide a count of providers who received the education as a measure of reach and description of uptake by discipline.

Data Analysis Plan

Aim #1: Analysis of Effectiveness for Improving Processes of Care. Analyses of chart abstraction data will begin by summarizing demographic variables and process of care endpoints with descriptive statistics and graphs. A key aspect of the descriptive statistics, as well as the analytic methods, will be identification of individuals as pre-implementation or post-implementation deaths within a hospital. Analysis of the primary endpoint (proportion of patients with an order for pain medication at the time of death) and secondary endpoints for the 48 randomized VAMCs will rely upon Generalized Estimating Equations (GEE) as developed by Zeger and Liang. Given the nature of the binary outcomes of this grant, one might assume that chi-square

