analyses or logistic regression could be used to analyze the resulting data. However, such an approach would be wrong. Because the probability of receiving an order for opioid naturally varies by hospitals, outcomes for individuals nested within a hospital are actually correlated. This correlation, called the intra-class correlation coefficient (ICC), violates a key assumption of chi-square analyses and logistic regression. Any variance estimates derived without taking into consideration the clustering effects are typically biased downward. GEEs, which can be thought of as logistic regression accounting for the clusters and the ICC, correctly estimate the variance of treatment effect as long as 30 or more clusters are used.

In order to test whether the Enhanced Implementation Approach leads to a higher proportion of patients having desired outcomes compared to the Basic Implementation Approach, GEE analyses of the post-implementation data will include an explanatory variable indicating to which arm the hospital was randomized. These simple GEE models, to be developed separately for the primary and each secondary outcome, will produce an unadjusted 95% confidence interval for the odds ratio for the outcome at time of death within an Enhanced Approach hospital relative to a Basic Approach hospital. If the hypothesized effect of Enhanced Approach leading to higher proportions of desired endpoints is true, then these confidence intervals should completely exceed an odds ratio of 1. Although confounding should be minimized due to the use of randomization of VAMCs, multivariable GEE models will be developed to incorporate patient characteristics that have been identified in our previous studies to be associated with the outcomes [(age, race, terminal illness, location of death)]. The justification for multivariable models is two-fold. First, inclusion of the covariates will adjust for any potential imbalance remaining after randomization. Second, inclusion of covariates should allow for greater precision in estimating treatment differences. As with the simple models, it is anticipated that these adjusted 95% confidence intervals should completely exceed an odds ratio of 1 for the endpoints. Add [name]'s section

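### Does the looser wording of the primary endpoint in the analysis plan change the outcome that is tested, or undo the stated 86% power?

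*Combined protocol and SAP*

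**What the plan says.** The primary endpoint is described in several places in the combined protocol and SAP.

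- **Measurement, Aim #1, Endpoints.** The formal definition, with the term in bold: the primary endpoint "will be presence of an active order for opioid medication at the time of death". On other drugs it adds: "In addition to the primary endpoint, we will abstract orders for and administration of antipsychotic medications for delirium or nausea and vomiting". The list continues with benzodiazepines and drugs for secretions.
- **Power.** The calculation draws on BEACON data for the primary endpoint, described as "change in proportion of patients with an active opioid order at time of death". The same section then sets the contrast as the post-intervention share of patients with an active opioid order, 0.65 in the Basic group and 0.70 in the Enhanced group.
- **Data Analysis Plan, Aim #1.** GEE is assigned to the outcomes in a sentence that begins "Analysis of the primary endpoint (proportion of patients with an order for pain medication at the time of death". Shortly afterwards, the same paragraph explains the need for GEE: "Because the probability of receiving an order for opioid naturally varies by hospitals, outcomes for individuals nested within a hospital are actually correlated".
- **Background, account of the BEACON trial.** The predecessor's list of primary endpoints starts with "proportion of patients with an order for opioid pain medication at time of death".

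**The concern.** The sentence that ties the primary endpoint to its model drops two qualifiers, opioid and active. Pain medication is a wider class than opioids. The Endpoints paragraph chooses opioids partly because they also treat dyspnea, so the two terms are not interchangeable.

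If the wider class were analysed, three things would be at stake. Patients with only a non-opioid order would score as successes, which could dilute a real shift towards opioid availability. The 0.65 and 0.70 used for power would no longer describe the tested variable. And two definitions of a primary outcome in one governing document would leave room to choose between them once results are known. The Power section's reference to a change in proportion looks like a third version, because the model compares post-implementation proportions only.

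**Working it through.** **1. Reproduce the plan's power for the opioid endpoint.** Inputs from the Power section: 24 sites per arm, 100 patients per site on average, 2,400 per arm, proportions 0.65 and 0.70, alpha 0.05, ICC 0.005. Sidedness is not stated; two-sided is assumed.

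- Design effect = 1 + (100 − 1) × 0.005 = 1.495
- Effective n per arm = 2400 / 1.495 = 1605.4
- Null standard error, with mean proportion 0.675: √(2 × 0.675 × 0.325 / 1605.4) = 0.01653
- Alternative standard error: √((0.65 × 0.35 + 0.70 × 0.30) / 1605.4) = 0.01651
- Power = Φ((0.05 − 1.96 × 0.01653) / 0.01651) = Φ(1.066) = 85.7%

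This matches the stated 86%. A one-sided test would give 91.6%, so two-sided is the reading that fits. The Basic proportion of 0.65 is also close to the 64.2% with an active opioid order in BEACON's 2005 baseline data (Background), so the calculation is plainly about opioids.

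**2. What a literal reading would do.** The documents give no rate for any pain medication, so this can only be illustrated. Suppose a share f of patients without an opioid order, equal in both arms, has another analgesic order, and the ICC is unchanged. Then Basic = 0.65 + 0.35f, Enhanced = 0.70 + 0.30f, and the difference is 0.05(1 − f).

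| f | Basic | Enhanced | Difference | Power |
|---|---|---|---|---|
| 0 | 0.650 | 0.700 | 0.050 | 85.7% |
| 0.1 | 0.685 | 0.730 | 0.045 | 80.1% |
| 0.2 | 0.720 | 0.760 | 0.040 | 73.4% |
| 0.3 | 0.755 | 0.790 | 0.035 | 65.8% |
| 0.5 | 0.825 | 0.850 | 0.025 | 48.4% |
| 0.7 | 0.895 | 0.910 | 0.015 | 29.9% |

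Suppose instead that a 5-point difference holds at a higher base rate. Power is then 88.8% (0.70 v 0.75), 92.4% (0.75 v 0.80) or 96.2% (0.80 v 0.85). The direction depends on an assumption that the documents do not settle.

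**3. Which variable would an analyst use?** Four points in the text agree.

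- The disputed words are a gloss in parentheses on a term that the Endpoints paragraph defines.
- The reasoning that follows in the same analysis paragraph is about the opioid order ("probability of receiving an order for opioid naturally varies by hospitals").
- BEACON's wording had the word opioid in front of pain medication. Removing that one word gives almost exactly the disputed phrase.
- The drug orders listed for abstraction beyond the primary endpoint include no non-opioid analgesic.

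The missing word active carries little weight. BEACON's endpoint list also omits it, while the BEACON results report an active opioid order. An order counted at the time of death is naturally one in force then.

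**4. The change wording.** It appears where the Power section describes data from BEACON, a before-and-after study. The contrast given next is explicitly post-intervention, and it matches the post-implementation GEE model.

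**The case for a change.** The strongest reply is that a primary endpoint should have a single definition, and that the sentence assigning it to a model is the wrong place for loose language. The clustering remark shows intent but is not a definition. The abstraction tool is BEACON's and is not reproduced in the document, so collection of non-opioid orders cannot be excluded.

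The change wording would also matter if it were taken as the test. Assume both arms at 0.65 at baseline, a 5-point difference afterwards in the Enhanced arm only, and 100 deaths per site in each period. The variance of the difference in change is then (3 × 0.2275 + 0.21) × k / 2400 = 0.8925k / 2400. The factor k is 1.495 if site effects are uncorrelated between periods and 0.995 if they are perfectly correlated. The standard errors are 0.0236 and 0.0192, and power is Φ(0.16) = 56% and Φ(0.64) = 74%.

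What stands is that the wording is inconsistent and that the tool cannot be inspected. The rest does not carry. The formal definition, the power basis and the analysis paragraph's own reasoning all point to opioids, so there is little real latitude to pick another outcome after the fact. The 56% to 74% belongs to a test that the plan does not specify. Whether to adjust for baseline is a separate design question.

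**Conclusion.** This is a clerical slip with no consequence for the trial. An analyst who follows the document's own definition will test the active opioid order among post-implementation deaths, and for that endpoint the 86% is right (85.7%, two-sided, ICC 0.005). The power losses under a broader endpoint rest on a share f that no document gives, taken as equal in both arms, and on an unchanged ICC; another equally undocumented assumption raises power. Nothing in the documents shows that non-opioid orders would be counted.

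Aligning the parenthesis with the Endpoints paragraph would be tidy, but it would leave the data collected, the model, the sample size and the conclusion as they are. The judgement assumes that the formal definition takes precedence over a parenthetical paraphrase. It would need another look only if the abstraction form turned out to code any analgesic order as the primary outcome.

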Several health services research (HSR) areas focus on improving patient quality of care by changing provider behavior. For instance, academic detailing, audit and feedback, benchmarking, continuing medical education (CME), and computerized reminder systems are all methodologies used to change provider behavior. The literature is consistent in reporting that interactive techniques are the most effective at changing physician care and patient outcomes. Clinical practice guidelines and opinion leaders are less effective. However, there is mixed evidence that these interventions alone can change and sustain behavior. The literature is clear that there does not appear to be a “magic bullet” in changing provider behavior, but that multi-modal interventions may be more effective compared to a single intervention methodology.

The proposed study will use a multi-modal approach to changing practice patterns for end-of-life care. This will be accomplished in part by offering an intervention that includes three core adult learning and development concepts: 1) training will be timely, relevant, insightful, practical and useful; 2) it will employ experiential learning and action learning strategies, methods and practices; and, 3) the central focus will be on participants’ interaction and collaboration. Specifically, using the PRECEDE phases of the conceptual framework, 1) providers will be predisposed to make the desired changes in practice through intensive case-based and experiential training and by utilizing in-house “change agents”; 2) providers will be enabled to change by providing them with a computerized clinical support tool, as well as a packet of written educational materials; and, 3) the changes in provider practice will be reinforced through structured consultation with trainers.

The two groups will receive the *same* Pre-Implementation Preparation and the same Education Intervention Packet Materials. They will *differ* on the implementation approach used to deliver the education intervention.

Table 1

| Components of Comfort Care Education Intervention/Implementation | |
|---|-----------------------------------|
| Teleconference | Train-the-Champion |
| A. Pre-Implementation Preparation | A. Pre-Implementation Preparation |

| | |
|---|---|
| Communicate with administrative leaders | Communicate with administrative leaders |
| Communicate with PCCT members | Communicate with PCCT members |

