Environmental Changes. Environmental endpoints will include orders for fans for dyspnea, nasogastric tubes, intravenous lines infusing, and restraints, and location of death (intensive care unit versus palliative care unit versus other). It is often appropriate to reduce the use of nasogastric tubes and infusing IV or other medical instrumentation that is no longer associated with benefit, but often associated with physical discomfort from the devices. Environmental changes should encourage family presence when available and appropriate. Regarding location of death, patients at the end of life are frequently in the ICU setting for at least some portion of their hospitalization. The ICU setting is associated with isolation from family and other support and the use of aggressive and invasive treatments that, at the end of life, may not be associated with clinical benefit, and have a high risk for iatrogenic harm. Many veterans are admitted to the ICU setting when this may not be consistent with goals of care before ultimately being transitioning to a comfort care approach.

Psycho-social-spiritual support. Indicators of psycho-social-spiritual support for patient and family will include pastoral care visits and family presence at or near the time of death.

In addition to the chart abstractions, the "Reminder Report" programming embedded in the CCOS will identify patients for whom the CCOS was used and will allow investigators to track use of the electronic CCOS by site.

Aim #2: Telephone Interviews with PCCT members

Telephone interviews will be conducted to qualitatively explore and formatively evaluate PCCT member experiences with and perceptions of the Basic and Enhanced Implementation Approaches. To ensure that multiple perspectives are included, we will invite all members of the PCCT from each site to participate in an interview. For sites in the enhanced Implementation group, it will be essential to include the two members of the team who attended the in-person, train-the-champion workshop, because they will be able to provide feedback on the workshop program. For sites in the Basic Implementation group, it will be important to include at a minimum, the lead physician and nurse, to provide feedback on the teleconference teaching session. Approximately 12-18 weeks following the end of the 4-month implementation window, interviews will be

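### The adjusted GEE controls for location of death, which is fixed after randomisation and is itself a secondary endpoint, so its odds ratio may not be the total effect of assignment

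*Combined protocol and SAP*

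**What the plan says.** In the Data Analysis Plan, Aim #1, the arms are compared on post-implementation deaths. The simple model is described thus: "GEE analyses of the post-implementation data will include an explanatory variable indicating to which arm the hospital was randomized". It is fitted for the primary and each secondary outcome.

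A multivariable GEE follows. Its covariates are described as patient characteristics "identified in our previous studies to be associated with the outcomes [(age, race, terminal illness, location of death"). Two reasons are given: precision, and that "inclusion of the covariates will adjust for any potential imbalance remaining after randomization". The plan then states that "it is anticipated that these adjusted 95% confidence intervals should completely exceed an odds ratio of 1 for the endpoints". It gives one covariate list for all outcomes and does not say which model governs if the two disagree.

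Under Measurement, Aim #1, Environmental Changes, the protocol says: "Environmental endpoints will include orders for fans for dyspnea, nasogastric tubes, intravenous lines infusing, and restraints, and location of death". The categories are "location of death (intensive care unit versus palliative care unit versus other"). The Endpoints paragraph places this group among the secondary endpoints, as "orders to facilitate environmental changes that enhance patient safety and comfort".

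**The concern.** Age, race and the underlying terminal illness are not plausibly changed by how a palliative care team was trained. Location of death is different. It is determined at the end of the patient's stay, after the hospital was randomised and trained, and the trial measures it because the intervention might move it. The plan therefore uses one variable both as an outcome of assignment and as a nuisance to be adjusted away.

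If location differs by arm, two things follow. Part of the arm's effect may run through location (for example, fewer ICU deaths), and conditioning on location takes that part out or, depending on signs, adds to it. In addition, location and orders may share unmeasured causes, in which case conditioning on location can create an association between arm and orders that assignment did not produce.

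The imbalance argument does not rescue this covariate. Sites may differ by chance in location mix; the Significance section mentions many new inpatient hospice-palliative care units. But a patient's post-implementation location cannot separate that chance difference from an effect of the arm. A reader told that the model corrects residual imbalance would credit any shift in the odds ratio to that correction.

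The shared list also means that, read literally, the adjusted model for location of death has location as its own covariate.

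**Working it through.** **The plan's own figure.** Inputs from the Power section: 2400 patients per arm (24 sites of 100), 0.65 v 0.70, ICC 0.005, alpha 0.05. The design effect is 1 + 99 × 0.005 = 1.495, and the effective size per arm is 2400 / 1.495 = 1605. Two-sided power for two proportions is 85.7%, which agrees with the stated 86%. That calculation contains no covariates. The planned odds ratio is (0.70/0.30) / (0.65/0.35) = 1.256.

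**Illustration: setup.** The documents give neither opioid-order rates by location nor an expected arm difference in location, so the following are assumptions: location reduced to ICU v non-ICU; 35% ICU deaths in Basic; a range of non-ICU:ICU odds ratios for an opioid order; a range of arm shifts in ICU share; no unmeasured common cause.

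1. Solve for the ICU and non-ICU order rates so that Basic totals 65%.
2. Solve for the common arm odds ratio within location so that Enhanced, with its shifted ICU share, totals 70%.
3. Share removed = 1 − (arm difference standardised to the Basic location mix) / 5 points. A negative value means inflation.

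**Worked case:** odds ratio 4, Enhanced 30% ICU.
- Basic: 0.35 × 0.4435 + 0.65 × 0.7612 = 0.650.
- Enhanced: 0.30 × 0.4868 + 0.70 × 0.7914 = 0.700.
- Within-location odds ratio: (0.4868/0.5132) / (0.4435/0.5565) = 1.19.
- Enhanced at the Basic mix: 0.35 × 0.4868 + 0.65 × 0.7914 = 0.6848, a difference of about 3.48 points. Share removed: 30.5% before rounding.

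**Results** (share removed; adjusted odds ratio):

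| Non-ICU:ICU odds ratio | Location equal by arm | Enhanced 2 points fewer ICU | Enhanced 5 points fewer ICU |
|---|---|---|---|
| 0.25 | 0%; 1.28 | −9.9%; 1.31 | −24.4%; 1.36 |
| 0.5 | 0%; 1.26 | −5.5%; 1.28 | −13.5%; 1.31 |
| 1 | 0%; 1.26 | 0%; 1.26 | 0%; 1.26 |
| 1.5 | 0%; 1.26 | 3.5%; 1.25 | 8.7%; 1.23 |
| 2 | 0%; 1.26 | 6.0%; 1.25 | 15.1%; 1.22 |
| 4 | 0%; 1.29 | 12.0%; 1.25 | 30.5%; 1.19 |

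If Enhanced has more ICU deaths, the signs reverse with similar sizes: at 2 points more, 10.2% is removed at 0.25 and the effect is inflated by 11.8% at 4. With Basic ICU shares of 25% or 47.4% (the two pilot values), the 5-point case gives 8.9–31.7% or 8.6–28.7% removed at odds ratios of 1.5–4.

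**Three categories.** Hold ICU at 35% in both arms, give ICU and other deaths the same order rate, and set the Basic palliative-care-unit share at 10%, 20% or 30%. Moving 2 or 5 points from other to palliative care unit in Enhanced removes 3.2–9.9% or 8.0–25.1% at palliative-care-unit:other odds ratios of 1.5–4, and inflates by about 6% or 15% at 0.5.

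**Unmeasured common cause.** Let the arm lower the log-odds of ICU death by 0.8, with no effect of arm or location on orders. Let an unmeasured factor, present in half the patients, change the log-odds of ICU death by 1.5 and of an order by +1.5 or −1.5. The total effect is then an odds ratio of 1.00, but the location-adjusted odds ratio is 1.08 or 0.92. These inputs are also assumed.

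**Precision given up by dropping location.** Wald test on the adjusted log odds ratio, logistic information matrix, design effect 1.495, location equal by arm: power 85.9% (odds ratio 1.5) to 88.9% (odds ratio 4) with the covariate, against 85.6% without it.

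**The case against.** The main inference is protected. The plan ties the test of Enhanced against Basic to the simple GEE, which is always produced and estimates the total effect; the adjusted model reads as supportive. This stands and confines the harm, although the plan never formally ranks the two models.

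The harm also needs an arm difference in location, and the documents predict none. Both arms receive the same preparation and materials and differ only "on the implementation approach used to deliver the education intervention". The pilot's fall in ICU deaths, 47.4% to 25%, was a one-site before-after result for a wider program. BEACON, with 6,066 records and location among its primary endpoints, does not name location among the effects significant after trend adjustment, and its contrast was wider than Enhanced v Basic. This stands too: whether any bias will arise is unknown.

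Two limits apply to the illustration. First, odds ratios are non-collapsible: with location equal by arm and an odds ratio of 4, the adjusted odds ratio is 1.29 against 1.26 with no bias at all. So a gap between the simple and adjusted odds ratios does not by itself show conditioning on a consequence of assignment; the share removed, on the standardised risk scale, is the cleaner measure. Second, the location table assumes no unmeasured common cause, so its ranges are not bounds.

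Finally, the Aim #1 analysis text ends with a note that a section is still to be added, so it may be unfinished. That does not cure the covariate list as written.

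**Conclusion.** The concern holds. A post-randomisation endpoint sits in the covariate list of the adjusted models, and the stated imbalance rationale does not work for it. That much follows from the text alone. Whether the adjusted odds ratios will in fact be distorted depends on location differing by arm, and the documents fix neither the sign nor the size. Under the assumptions shown, a 2-point arm difference in ICU deaths alters the 5-point effect by up to about 12% in either direction, and a 5-point difference by up to about 30%; with no difference, nothing is removed. The simple GEE and the power calculation are untouched. It should be fixed, but it does not threaten the primary comparison.

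**What to change.** Delete location of death from the covariate list for every outcome, keeping age, race and underlying terminal diagnosis. If adjustment for site differences in location is wanted, use each site's pre-implementation location mix from the 9-month baseline abstraction; that period precedes training, so the mix cannot carry its effect. Analyse post-implementation location only as an endpoint, or in an analysis labelled exploratory or mediation.

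The cost is one line in the analysis plan and no new data. Some precision may be lost in the adjusted model: at most about 3 points of power (88.9% to 85.6%) under the assumptions above.
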